## **10. Adverse Events**

Adverse events will be reviewed by the Principal Investigator, Research Monitor and the DSMB and will be reported to the Human Research Committee within the required time frame and to all participating investigators according to the Partners Human Research Committee guidelines.

Underlying diseases or conditions are not reported as AEs unless there is an increase in severity or frequency during the course of the investigation. Death should not be recorded as an adverse event, but should only be reflected as an outcome to the applicable AE that led to the death.

## **11. Risk Benefit Analysis**

### **11.1. *Known and Anticipated Risks***

We anticipate the risk to the subjects due to participation in this study to be low. Subjects who have satisfied the inclusion/exclusion criteria as outlined in the protocol will be eligible for enrollment. All subjects will be treated according to the standard of care guidelines for their condition according to the medical staff. For the experimental portion of the procedure, after consent has been obtained, subjects will undergo approximately 20 minutes of exposure to the Photomedex Helmet for at least 2 time points and up to 3 time points. The first helmet application will take place in the inpatient unit or in the ED observation unit. If the subject is admitted as an inpatient he/she may have up to 2 additional helmet applications no sooner than 12 hours after the previous helmet application. If the subject is discharged from either the inpatient unit or the ED observation unit prior to his/her 2nd helmet application, he/she will have up to 2 additional helmet applications no sooner than 12 hours after the previous helmet application arranged either through a follow up visit.

In order to optimize the LLLT, we would like to shave the head. This will be optional to the surrogate/subject and will be explained at the time of informed consent. There is a slight potential risk of a small cut to the head during shaving of the head. In addition, there is a small amount of radiant heat that is generated by the Photomedex helmet. The helmet will be efficiently cooled with fans but depending on the skin and hair color of the subject the temperature of the scalp may be raised enough to be perceived as warmth. In addition, the subject's core temperature will be monitored and in the unlikely event that the temperature increases more than 0.5 C the helmet will be removed.

Following initial exposure to the Photomedex Helmet, a baseline MRI will be performed at the earliest opportunity as soon as the patient is able to lay flat for 1 hour and the scanner is available for scheduling. If the subject is admitted to an inpatient unit, he/she will have the first MRI scan in Lunder 6 at the MGH Main Campus. If the subject is discharged from the ED Observation unit, he/she will have the first MRI scan at the Martinos Center in Charlestown.

For subjects admitted to the inpatient unit, there is a small risk of complication associated with moving the subject from the ICU to radiology for MRI. The most common complications are related to inadvertent dislodgement of tubes and lines or related to temporary disconnection from the mechanical ventilator. These complications are inherent in any travel out of the ICU. If the risk of travel complications is deemed by the clinical (non-study) team to be too high, MRI for the purposes of this study will be deferred until a later date. The FDA considers investigations using MRI software and hardware to be non-significant risk, as long as they are operated within

FDA specified parameters. All MRI studies will adhere to the FDA approved for the Siemens 3T system used in this research. These safety parameters include static magnetic field, time varying magnetic fields (dB/dt), specific absorption rate (SAR), and acoustic noise levels.

### 11.2. *Risk Minimization*

This study involves the application of the Photomedex helmet for delivery of low-level laser light using LED cluster heads. The risks to the subject have been minimized by choosing an exposure that has been shown to be effective but does not exceed accepted standards. The exposure generated by the Photomedex Helmet is well below the accepted ANSI standard for the safe use of lasers and laser systems [ANSI Z136.1]. The accepted maximum permissible exposure (MPE) between 10s-10,000s is 332 mW/cm^2. The Photomedex helmet will be operating for approximately 1200s and has a power density of 36mW/cm^2 which is approximately 10 times below the accepted standard. In addition, the output fluence of our device per treatment session (43 J/cm^2) is at approximately half of that used in the NEST-1 trial (82 J/cm^2) with the Photothera device by Lampl et al in stroke patients. In this study there were no adverse events found to be significantly related to the application of the Photothera device [26]. We will also monitor the temperature of the subjects during application of the Photomedex helmet to ensure that application of the LLLT does not increase the temperature of the subject more than 0.5 C. If a temperature above this is reached the Photomedex helmet will be removed.

This study also involves MRI of the brain without intravenous contrast. There is no additional risk to the subject associated with these proposed MRI sequences, above those of a conventional MRI that is routinely performed on these patients for clinical workup. The FDA considers investigations using MRI software and hardware to be non-significant risk, as long as they are operated within FDA specified parameters. We will ensure all imaging will take place according to the FDA specified parameters for the Siemens 3T system.

We will employ measures throughout the course of this study to minimize risks to subjects choosing to participate. All efforts will be made to minimize potential risks by:

- Providing training on the investigational equipment prior to use
- Defining inclusion/exclusion criteria clearly to ensure only appropriate subjects are enrolled.
- Ensuring that the treatment of the subject is consistent with current medical practices.

## **12. Monitoring**

The Principal Investigator will make necessary efforts to ensure that this trial is conducted in compliance with GCPs and all applicable regulatory requirements.

### **12.1. *Data and Safety Monitoring***

The PI will be responsible for overseeing all aspects of the study including: ensuring that the study is conducted according to the IRB-approved protocol, performing monitoring and confirming compliance of the study, and protecting the rights, safety and welfare of the subjects. Should the PI at any point feel that the health and well being of the subject is compromised the study procedures will be immediately suspended.

Data will be collected by the appropriate study staff, such as research fellows from the Department of Trauma, Emergency Surgery and Surgical Critical Care. Case report forms will be kept securely in the electronic Partners Redcap Database. In addition, electronic data will be stored on a Password Protected computer system and backed up onto a secure server location. Only the PI and research team will have access to the database, and identifying information will not be released. The data will be reviewed regularly by the designated study staff and the PI will regularly review the data and findings with the study staff during a regularly held research meeting. Throughout the duration of the study, the PI will perform ongoing evaluation of subject safety data in order to identify AEs and trends as soon as possible. The PI will be responsible for determining whether the research should be altered or stopped. In addition, de identified image MRI image data will be shared with external collaborators in order to perform quantitative image analysis through a customized computational algorithm. The data will have all identifiers removed and will be transferred to the collaborator by a study staff member.

A designated study staff member will be responsible for gathering post-procedure follow-up data on the subject. The subjects will be followed until discharge. We will also follow-up with the patient 3 and 6 months after injury. A follow up phone call will be completed at 12 months.

In order to review the data in an unblinded fashion, we will establish a DSMB of experienced specialists from Trauma, Neurology, Radiology, Rehabilitation at MGH and Spaulding, and the Wellman Center at MGH who are not conflicted or study staff members to review the safety data. The DSMB will review the data collected after the first 10 subjects have been enrolled. The DSMB will make a recommendation as to whether or not the study should continue. If the DSMB recommends continuation of the study, subsequent DSMB review of data once per year.

Additionally, [name] MD, a neurologist at MGH and member of the DSMB will serve as an independent research monitor for the study. He will review the research protocol with the

investigators, review the monitoring plan, and review study data. If the research monitor is concerned for the safety and well-being of the subjects he/she will have the authority to stop the research protocol in progress, remove individual human subjects from a research protocol, and take whatever steps are necessary to protect the safety and well-being of human subjects until the IRB can assess the monitor's assessment. The research monitor will review all unanticipated problems involving risk to subjects or others, device-related serious adverse events and all subject deaths associated with the protocol. At a minimum, the research monitor must comment on the outcomes of the event or problem and in case of a device-related serious adverse event or death, comment on the relationship to participation in the study. The research monitor must also indicate whether he/she concurs with the details of the report provided by the principal investigator. The research monitor will provide an unbiased written report Reports for events determined by either the investigator or research monitor to be possibly or definitely related to participation and reports of events resulting in death will be promptly forwarded to the USAMRMC ORP HRPO.

#### **12.2. *Monitoring and Quality Assurance***

Monitoring of the study data will be made to ensure that all aspects of the current, approved protocol/amendment(s) are followed. Original source documents will be reviewed for verification of data. A monitoring log will be completed for proper documentation. A device accountability will also be kept for the Photomedex Helmet used in the study.

Subject data will be collected via case report forms and will be recorded in a Partners RedCap Database designed specifically for the study. The PI will ensure the accuracy and completeness of the recorded data and will provide his/her signature to verify. If any discrepancies are found during monitoring of the data, confirmation of the correct information will be made by the PI by signature and a note to file description will be generated.

Light Therapy for Moderate Traumatic Brain Injury

NCT02233413

Statistical Analysis

6.26.20

Statistical Analysis

All statistical analyses were performed using R Language for Statistical Computing (version 3.6.0). Differences and relations were considered statistically significant at $p < 0.05$. All results are presented as mean + standard deviation (S.D.) unless noted otherwise. Baseline differences across groups were compared via using one-way ANOVA for continuous variables (e.g., Age, RPQ scores) and via Chi-Square test for categorical variables. To test neuroreactivity of LLLT via its effect on the diffusion tensor parameters, we used a linear mixed effect (LME) model with treatment (light therapy vs. sham) and time point (acute, early sub-acute, late sub-acute) as fixed effects, and tract and time point nested within each patient as random effects. All patients with at least one MRI were included in this analysis. Conformity of the data to statistical assumptions were checked by investigating QQ plots of the data. LME models, which are akin to multiple regression models that can account for correlations due to repeated measures, have several advantages in this context. LME modeling allowed us to pool all our data --- i.e., across treatment groups and three time points, as well as across all 18 tracts --- to examine relationships robustly. Moreover, because the LME model allows partially repeated measures, it can accommodate data from subjects with missing timepoints (e.g., missing MRI sequences). In addition, the LME model treats each timepoint as a separate variable. Therefore, any baseline difference in DTI parameters across the LLLT and sham groups did not confound the overall analysis enabling one to robustly identify differences in DTI parameters across the treatment groups while explicitly accounting for repeated measurements, within-tract and within-subject correlations, and missing time points.

A similar LME model (treatment group and time point as fixed effects, and patient as a random effect) was used to test for the effect of LLLT on clinical symptoms). The p values for the fixed effects in the LME model were calculated using type III analysis of variance table with Satterthwaite's degrees of freedom method.

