### 1.3. *Clinical evidence of efficacy and safety supporting a pilot clinical study*

Positive preclinical results motivated a first clinical study of LLLT for stroke. The results of that study, NEST-1, were published in 2007 [26]. This double-blinded placebo controlled study tested the efficacy and safety of LLLT across 120 patients. Light was delivered through a handheld device placed against the shaved scalp. The device was moved to 20 predetermined locations, and held at each location for a duration of 2 minutes. The treated group received LLLT at an average of 16 hours after stroke. Patients were evaluated based on the NIH stroke severity (NIHSS) scale at baseline, +5 d, +30 d, +60 d, and +90 d after stroke. The treatment group in this study showed improved NIHSS over this time-frame ( $p = 0.021$ ). In a follow-up study of 660 patients (NEST-2) [27], a post-hoc analysis of moderate to moderate-severe stroke subpopulation ( $n = 434$  patients) showed a statistically significant NIHSS benefit ( $p = 0.044$ )[40]. A third study (NEST-3) targeting a moderate stroke populations is currently underway.

In addition to providing clinical evidence that transcranial LLLT is effective in treating brain trauma, the NEST-1/2 studies demonstrated a very strong safety profile for the intervention. Detailed safety analyses were performed in both studies of over 700 combined subjects and concluded that LLLT was not associated with any risks within the stroke population of the studies.

Transcranial PBM has not to date been studied as an adjunctive treatment for acute moderate TBI and we would like to conduct a pilot study to assess feasibility. We see this as the first of a series of studies to explore whether LLLT might be useful as a safe and effective treatment for moderate TBI.

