## **9. Statistical Methods**

In this pilot study, the study size is limited by number of recruitable patients admitted to MGH emergency department. Based on prior-year admission records, the itemized inclusion/exclusion criteria, and an assumed 80% consent rate, we estimate an average enrollment of 1 patient per week.

The sufficiency of these enrollments toward powering the primary hypothesis (DTI outcome measure) is presented below. These calculations require an assumption of the acute LLLT therapeutic effect size, which is unknown and cannot reasonably be estimated from either the preclinical data or the clinical stroke studies. Our analysis is based on an assumed effect size of 25%.

The coefficient of variation for fractional anisotropy (FA) is based on data from a cohort of 12 mild to moderate TBI patients scanned using quantitative MRI [30]. For this cohort, FA was measured in 16 regions of the brain. The coefficient of variation (CV), defined as the ratio of mean to the standard deviation, was 53.45%. However, this study included mild to moderate. With the more narrow inclusion of moderate TBI, we estimate a FA CV of 40% (based on clinical and research experience of the investigators, and knowing that the CV for healthy volunteers is 25%). The required sample size for detecting changes in FA associated with acute LLLT [31] is then 82 (41 patients in each group). We note that other diffusion parameters (mean diffusivity, axial diffusivity, and radial diffusivity) featured much lower CV, and would be sufficiently powered with this sample size.

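### The SAP tests several diffusion parameters and symptoms at unadjusted p<0.05 without ranking them or calling them exploratory, although the Protocol's 82 is sized on one FA comparison

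*SAP*

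**What the plan says.** The SAP has one threshold for all comparisons: "Differences and relations were considered statistically significant at" p<0.05. The imaging model has a stated purpose, "To test neuroreactivity of LLLT via its effect on the diffusion tensor parameters", but the parameters are not listed and FA is not named. Its listed fixed effects are treatment and time point, and it pools three time points and 18 tracts. A similar model "was used to test for the effect of LLLT on clinical symptoms", with no score named; RPQ appears only as an example of a baseline variable. On inference the SAP adds that "The p values for the fixed effects in the LME model were calculated using type III analysis of variance table", without singling out a term. It mentions no adjustment for multiple tests and no primary, secondary or exploratory ranking.

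Protocol Section 9 says the adequacy of enrolment for "powering the primary hypothesis (DTI outcome measure) is presented below". It then computes "The required sample size for detecting changes in FA associated with acute LLLT" as 82, or 41 per group. It adds that "other diffusion parameters (mean diffusivity, axial diffusivity, and radial diffusivity) featured much lower CV, and would be sufficiently powered with this sample size". The Protocol Synopsis places MRI and clinical response under the secondary endpoint. Section 1.3 describes a pilot to assess feasibility: "We see this as the first of a series of studies to explore whether LLLT might be useful".

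**The concern.** A reader of the two documents cannot tell which result would count as evidence of neuroreactivity. Section 9 leaves four candidate diffusion parameters, and the SAP gives each the same unadjusted threshold. If the claim can rest on whichever parameter falls below 0.05, its error rate is not the 5% that the threshold suggests. What is at stake is how far a significant diffusion result can be relied on when the next study in the planned series is designed. The sample size is also affected, because 82 carries no allowance for more than one test.

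**Working it through.** **1. Reproduce the sample size.** Inputs from Protocol Section 9: effect 25%, FA coefficient of variation 40%. Section 7 gives 1:1 allocation. Two-sided 0.05 and 80% power are assumed, since the Protocol states neither.

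n per group = 2 × (1.960 + 0.842)² × (0.40/0.25)² = 2 × 7.85 × 2.56 = 40.2, so 41 per group and 82 in total. This matches the Protocol. The 82 is therefore consistent with one comparison of one parameter at 0.05.

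**2. Count the treatment tests that the SAP describes.** Only one listed fixed effect carries treatment: the main effect, pooled over time points and tracts. That is one treatment test per diffusion parameter. The 18 tracts add no tests because they share a model. Taking the parameters in Section 9 as the set gives k = 4. This is an assumption, because the SAP does not list them.

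**3. Chance of at least one p<0.05 with no treatment effect.** The four test statistics are taken as standard normal with equal pairwise correlation ρ. The documents give no correlations, so a range is shown.

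P = 1 − ∫ φ(u) × [Φ((1.96 − √ρ·u)/√(1−ρ)) − Φ((−1.96 − √ρ·u)/√(1−ρ))]⁴ du

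| ρ | P(at least one of four) |
|---|---|
| 0.5 | 15.6% |
| 0.8 | 11.4% |
| 0.9 | 9.4% |
| 0.95 | 8.0% |

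For reference, independence would give 1 − 0.95⁴ = 18.5%. The parameters are probably strongly related, so the lower part of the table is the more plausible.

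**4. Cost of making all four confirmatory instead.** At 0.05/4 = 0.0125, with the FA assumptions, the step 1 formula gives 57.1, so 58 per group or 116 in total, against planned enrolment of up to 90. Two-sample t-test power at 41 per group and standardised effect 0.25/0.40 = 0.625 is 80% at 0.05 and 61% at 0.0125. These figures assume one value per patient. They are not the power of the SAP's mixed model, and Section 9 says the other parameters vary less than FA. They show why one lead test fits this trial better than a split threshold.

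**The case against.** The strongest reply is that this is a pilot. MRI and clinical response are secondary in the Synopsis, Section 1.3 describes a series of studies that begins here, Section 9 calls the effect size unknown, and neither document promises family-wise error control. That stands, and it limits the priority. It does not settle the matter: Section 9 also calls DTI the primary hypothesis, and the SAP declares significance at 0.05 without repeating the exploratory framing.

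Four stronger readings are tempting, and the documents do not support them:

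- **That the SAP departs from the Protocol by not leading with FA.** Section 9 sizes on FA but never formally ranks it above the other three.
- **That a lead time point is missing, or that tracts, scans and an interaction multiply the tests.** A main effect pooled over time points needs no lead time point. Separate tests at each scan are not described. A treatment-by-time-point interaction is neither stated nor excluded. Testing one would raise the figures above, but no amount can be charged to the plan as written.
- **That the SAP lets any one significant parameter establish neuroreactivity.** It does not say so; it only leaves the possibility open.
- **That the lead test would be chosen after the data were seen.** The past tense suggests the analyses had been run, but the SAP does not say what was known when it was written.

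**Conclusion.** The concern holds in a limited form. The SAP tests several unranked diffusion parameters and symptoms at unadjusted 0.05, while the planned size corresponds to one FA test. Reading any one of four significant parameters as neuroreactivity carries a false-positive chance of about 8% to 16%.

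That range rests on four parameters, one treatment test each, equal correlation between 0.95 and 0.5, no true effect, and the any-one-suffices reading. It illustrates the size of the problem and is not a bound. Symptom tests are outside the range and share the same threshold. The matter is worth correcting at low to moderate priority.

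**What to change.** In the SAP:

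1. List the diffusion parameters and symptom scores tested.
2. State whether a treatment-by-time-point interaction is in the model and, if it is, which one treatment term is the lead test.
3. State whether any results had been seen when the text was written.
4. If none had, make the FA treatment effect from the stated model the single lead DTI test at two-sided 0.05, citing Protocol Section 9 as the basis for FA. Report MD, AD, RD and symptom scores as exploratory with estimates and 95% confidence intervals, or with Holm-adjusted p-values over a stated set of tests.
5. If results had been seen, label all DTI and symptom results exploratory, FA included, and make no confirmatory claim of neuroreactivity.

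The cost is SAP wording and relabelling of reported results. No new data are needed, and 82 stands as the size for a single FA comparison. The downside is that MD, AD, RD and symptoms lose an unadjusted label of significance, and FA's result becomes exploratory too if results had already been seen.

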### 7.1. *LLLT Photomedex Helmet Device Application*

In order to maintain blinding, a study staff member not associated with analysis of the study will create a randomization code and assign treatment via an envelopment randomization system. The study staff member in charge of applying the Photomedex helmet will open each randomization envelop and once the clinician deems it is acceptable, subjects will undergo approximately 20 minutes of exposure to the Photomedex helmet within 72 hours after injury. If the subject is assigned to the sham group the LEDs will not be activated. Because the helmet uses NIR light that is invisible to the human eye, clinical staff within the room will not be able to detect whether the LEDs are activated.

The Photomedex helmet will be used up to 3 times for each subject. The first application will be as soon as possible after injury, within 72 hours. Follow up applications of the Photomedex helmet will be applied for up to 2 additional time points no sooner than 12 hours after the previous helmet application. If the subject is discharged from the hospital prior to the second helmet application, a follow up helmet application will be scheduled. If the subject wishes to have the option to complete in-person visits at his/her place of residence or another location, they will indicate this by signing the LLLT Out of Hospital Follow Up Consent Form at the time they enroll in the study.

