### 7.2. *Magnetic Resonance Imaging*

Following the 1st Photomedex helmet application, a baseline MRI will be performed, at the earliest opportunity, as soon as the subject is able to lay flat for 1 hour and the scanner is available for use. If the subject is admitted as an inpatient the scan will take place at Lunder 6 on the MGH Main Campus. If the subject is discharged from ED Observation prior to the first MRI, then the baseline MRI will take place at the Martinos Center at the Charlestown Campus. It is anticipated that the MRI will take place within 24-48h hours after enrollment and the scanning protocols themselves will take approximately 60 minutes to perform. Taking into account any necessary set up time before, during and after scanning the total time for the MRI will be approximately 60-90 minutes. If the subject is unable to undergo research-related imaging, this will be deferred until it is safe and feasible. This baseline MRI is performed

following the first application of light therapy because of the need to deliver light therapy as soon as possible after injury, and the clinical challenges of performing MRI within the first 12 hours. A designated study staff member will be responsible for gathering post-procedure follow-up data on the subject. The subjects will be followed until discharge.

Imaging protocol (for baseline and post-treatment imaging):

Subjects will be asked to lie still in a supine position for the duration of the imaging session. Head motion will be minimized during image acquisition by the use of a dedicated head coil with holder.

The MRI protocol may include the following sequences:

- 1) Localizer/Auto-aligned scout
- 2) High resolution T2 weighted imaging
- 3) FLAIR (Fluid attenuated inversion recovery) imaging
- 4) High resolution 3D T1 weighted isotropic imaging
- 5) Susceptibility-weighted imaging (SWI)
- 6) Diffusion tensor imaging (60 encoding directions)
- 7) BOLD EPI functional MRI for the evaluation of resting state functional connectivity (FC) within and between motor, visual, auditory, dorsal attention, executive control, salience and default mode networks.
- 8) Arterial Spin Labeling (ASL) brain perfusion imaging.

No contrast agent or other pharmacological substance other than ones clinically required for the subject will be given.

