### **7.3. Follow Up**

Follow up visits will be coordinated by the study staff with the subject and/or surrogate.

Additional MRI scans will be performed at approximately 14-21 days and 3 months after injury for image analysis (see Section 7.2 for Imaging Protocol). At day 7 a follow-up phone call will be made to check on the subject after discharge for symptoms reporting. Clinical follow-up visits will take place at approximately 14-21 days, 3 months and 6 months post-injury. The 6 month follow up can be completed in person or over the phone since it does not require in person physical evaluation. A follow-up phone call will also be performed at day 7 and at 12 months.

For subjects who are discharged from the ED's 24-hour Observation Unit, the same follow up procedures will apply. Additionally, subjects in ED Observation who only received 1 helmet application will have up to 2 additional helmet application(s) performed by study staff at a follow up appointment. Throughout the study duration, subjects may be contacted by phone, email or mail by clinical research staff for study related reasons.

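### Neither mixed model lists a treatment-by-time term, so the treatment test is one gap averaged over visits, and the assurance that baseline differences could not confound it does not follow

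*SAP*

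**What the plan says.** The SAP (Statistical Analysis) describes the model for the diffusion tensor parameters as a "linear mixed effect (LME) model with treatment (light therapy vs. sham) and time point (acute, early sub-acute, late sub-acute) as fixed effects", with tract and time point nested within patient as random effects. For symptoms it says: "A similar LME model (treatment group and time point as fixed effects, and patient as a random effect) was used to test" the effect of light therapy. P values come from a type III table with Satterthwaite degrees of freedom. From the model's handling of each time point as its own variable, the SAP concludes that "any baseline difference in DTI parameters across the LLLT and sham groups did not confound the overall analysis".

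The protocol fixes the timing:

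- **Acute scan.** Section 7.2 places the baseline MRI "following the first application of light therapy because of the need to deliver light therapy as soon as possible after injury", and adds: "It is anticipated that the MRI will take place within 24-48h hours after enrollment".
- **Later helmet applications.** Section 7.1 allows "up to 2 additional time points no sooner than 12 hours after the previous helmet application".
- **Later scans.** Section 7.3: "Additional MRI scans will be performed at approximately 14-21 days and 3 months after injury for image analysis".

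Section 9 of the protocol gives only a sample size, which "is then 82 (41 patients in each group"), and no analysis model.

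**The concern.** An additive model forces the difference between arms to be the same at every visit. The documents do not contradict a constant gap, but they give reason to doubt it. The acute scan comes after at least one application, and some patients have more exposure to come while others do not. If the effect builds up, appears late or reverses, averaging dilutes or cancels it in the only treatment test described. Section 2 of the protocol aims to quantify the response, yet one averaged gap gives no estimate at any single scan.

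The baseline sentence is a separate matter. Categorical time removes only the visit means that both arms share. It does not remove a gap between arms at the acute scan, and that scan is one of the three outcomes. A chance imbalance there can therefore be read as a treatment effect, while the SAP tells the reader that it cannot.

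**Working it through.** **Inputs from the documents.** Protocol section 9: effect 25% of mean fractional anisotropy (FA), coefficient of variation 40%, 41 per group. Protocol section 7: allocation 1:1. SAP: three scans, significance at 0.05.

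**Assumptions.** Two-sided test; complete scans; one value per patient per scan (the 18 tracts are not modelled); SD 1 at each scan; equal correlation ρ between scans of 0.5 or 0.8.

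**Reproducing the plan's figure.** Standardised effect = 0.25/0.40 = 0.625. At 80% power (not stated in the protocol), n = 2 × [0.40 × (1.960 + 0.842)/0.25]² = 40.2, rounded up to 41 per arm and 82 in total. This matches and is not in dispute.

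**What the coefficient estimates.** With complete data the additive treatment coefficient is the mean of the three visit gaps, d̄ = (d₁ + d₂ + d₃)/3. Its standard error is √[((1 + 2ρ)/3) × (2/41)], which is 0.180 at ρ = 0.5 and 0.206 at ρ = 0.8.

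**Power.** Treatment test: noncentral t on 80 df. Interaction test: noncentral F(2, 160) with λ = (41/2) × Σ(dᵢ − d̄)²/(1 − ρ). Each range runs over the two values of ρ.

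| Gap at acute / 14-21 d / 3 mo (SD) | d̄ | Averaged treatment test | Interaction test |
|---|---|---|---|
| 0.625 / 0.625 / 0.625 | 0.625 | 85-93% | 5% |
| 0.4 / 0.6 / 0.625 | 0.542 | 74-84% | 15-33% |
| 0.3125 / 0.625 / 0.625 | 0.521 | 71-81% | 29-62% |
| 0 / 0.625 / 0.625 | 0.417 | 52-63% | 83% to >99% |
| 0 / 0.3125 / 0.625 | 0.313 | 32-40% | 71-98% |
| 0 / 0 / 0.625 | 0.208 | 17-21% | 83% to >99% |
| 0.4 / 0 / −0.4 | 0 | 5% | 91% to >99% |

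A mixed-model simulation (200 runs per pattern, ρ = 0.5) agreed. For a 3-month-only effect the averaged test rejected in 20% of runs and the interaction in 85%.

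A single-scan contrast has 80% power for 0.625 SD. Its 95% confidence interval half-width is 1.99 × √(2/41) = 1.99 × 0.221 = 0.44 SD.

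**Baseline claim.** Suppose there is no treatment effect and a chance gap g at the acute scan. The expected gap at each later scan is ρg, so the expected coefficient is g(1 + 2ρ)/3. A one-standard-error gap is g = √(2/41) = 0.221 SD.

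- ρ = 0.5: 0.221 × 2/3 = 0.147 SD, and 0.147/0.625 = 24% of the planning effect.
- ρ = 0.8: 0.221 × 2.6/3 = 0.191 SD, and 0.191/0.625 = 31%.

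The conditional false-positive rate is 2.4% (ρ = 0.5) or 0.2% (ρ = 0.8) at a one-standard-error gap, and 29% or 39% at two standard errors.

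**Symptom model.** The SAP does not list its visits. If the baseline symptom score (RPQ) is one of k time points and the effect is constant afterwards, the coefficient shrinks to (k − 1)/k of it. That is 2/3 for three time points, 3/4 for four, and 5/6 if baseline and all five contacts in protocol section 7.3 are used.

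**The case against.** The strongest reply is that the evidence is silence in a short prose summary. Naming two factors as fixed effects does not exclude their interaction. A type III table hints at one, since type II and type III tests coincide in a main-effects model. If the interaction was fitted, the power table describes a model that was never run. This stands as a limit: the finding concerns the text as written. Even then, the treatment main effect would still carry an acute-scan gap, so the baseline sentence would still need correcting.

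Second, under 1:1 randomisation the additive test keeps its 5% level on average, and at a one-standard-error gap its conditional false-positive rate is below 5%. That is correct. The complaint is that an observed imbalance shifts the estimate and that the reader is told otherwise. An inflated overall error rate is not claimed. Because the acute scan follows the first application, a gap there may also be an early effect, and the model cannot separate the two.

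Third, the time-averaged gap is a legitimate estimand. It is the more powerful choice for a constant effect, and the documents specify no time course. This also stands. The late-only and reversing patterns are illustrations, and the loss for a partial acute effect is modest. It is a reason to keep the averaged difference, but not to report it alone.

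Finally, per-scan contrasts for FA and the three other diffusion parameters in protocol section 9 make 4 × 3 = 12 intervals. That multiplicity is a fair caveat for supplementary estimates.

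**Conclusion.** The concern holds for the text as written. Both models list treatment and time point only, and neither document supplies an interaction, a per-visit contrast, a change score or an acute-scan covariate. The loss of power is modest when much of the effect is already present at the acute scan (71-84%, against 85-93% for a constant effect) and large when it develops, comes late or reverses (5-63%). The statement that baseline differences could not confound the analysis is wrong for the listed terms, whatever the time course.

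The structural points need no numerical assumption. The percentages depend on the assumed correlation of 0.5-0.8, complete scans, the planned 41 per arm and one value per patient per scan. This should be fixed, because it governs how the main imaging and symptom results are read.

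**What to change.** - Give the fitted formula for both models. Add treatment by time point, or state it if it was already fitted.
- Report the interaction test and the light-minus-sham difference with its 95% confidence interval at each scan or visit. Keep the time-averaged difference beside them.
- List the visits in the symptom model.
- Remove or correct the sentence on baseline differences. Say that the acute scan follows the first application, so a gap there may be chance or early effect.
- If the additive model has already been run, label the additions post hoc. Present the per-visit intervals as supplementary and note their number.

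The cost is one model term, estimates from data already collected, and SAP wording. A non-significant interaction must not be read as proof of a constant effect, since its power is only 15-62% for the two partial-acute patterns above. A joint 3-df test of treatment plus treatment by time could be added as supplementary. It is non-directional, and under a constant effect it has 82% power against 93% at ρ = 0.5, and 70% against 85% at ρ = 0.8. It therefore need not replace the averaged test.
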